#### **Subgroup analyses**

The main subgroups that will be analyzed, in addition to the total population per protocol, will be adults and children.

#### **Endpoint analysis**

The primary endpoint of 1-year infection free survival rate will be estimated by the Kaplan-Meier method, the 95% confidence width for the survival rate will be estimated by the Peto method. The Kaplan-Meier survival curve will be presented.

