## 1 Introduction

### 1.1 Background and principle

Abnormal enlargement of part or all of subarachnoid space or ventricles, the abnormal accumulation of cerebrospinal fluid (CSF) in subarachnoid space or ventricles is called hydrocephalus. It is a circulation disorder of CSF caused by many pathological reasons. A shunt system mainly drains CSF from the accumulation site to the abdominal cavity, the lumbar cistern, and the atria through a catheter so as to address dilated ventricles and alleviate the pressure on the brain.

The earliest permanent CSF shunt operation occurred in 1893. A glass catheter was placed in a lateral ventricle of a patient with hydrocephalus, the end of which was placed under the skin. The head circumference of the patient was significantly reduced after the operation. The principle of modern shunt operation can be dated back to the 1870s. Ventriculo-peritoneal shunt operation had become a common treatment for hydrocephalus. China released *Specialist Consensus on the Standardized Treatment of Hydrocephalus in China* in 2013, which regarded CSF shunt as an important operation for hydrocephalus and proposed suggestions on technical key points.

However, in terms of the treatment of neurosurgical diseases, the incidence of complications of shunt operations is the highest, mainly including shunt infection, obstruction or rupture of a shunt catheter, displacement of an intracranial or abdominal shunt catheter, excessive or insufficient drainage of CSF, intracranial hemorrhage, and epilepsy. Infection is a common complication and important cause of revision. Its incidence rate is 3-29%. Approximately 90% of the cases occur within one year after the operation. If it is combined with ventriculitis, the mortality rate can be as high as 30-40%. For children, even if the infection can be controlled, long-term complications, such as epilepsy, cognitive impairment, and physical and delayed psychological development, may occur.

According to the analysis of recent literature, among a total of 8,588 shunt operations (3,291 cases with an antibiotic-impregnated catheter, 5,297 cases with a non-antibiotic-impregnated catheter), the postoperative infection of normal shunt system was 7.2%.

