## 10.2 General considerations

The primary analysis will be descriptive in nature and will be based on information in the data collection form.

The extraction of the data from the medical records will be done by the investigators who care for the patients; in this way, the possible limitation of the study that is normally observed in other studies of review of clinical histories in which the information can be interpreted incorrectly is minimized.

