## 10.3 Sample size

This study will provide infection free survival at 1 year for Hakim programmable shunt system and ensure 95% confidence bounds acceptable (half width < 5%). If  $N_0$  is the number of enrolled subjects, the number of infection free subjects after  $t$  years will be approximately:

$$N(t) = N_0 e^{-(r_1+r_2)t}$$

where  $r_1$  and  $r_2$  are the infection rate and the dropout rate respectively.

Following the Peto method, parameter estimation (e.g., infection free survival) in survival analysis will be performed. Defined  $S(t)$  as the survival rate at  $t$  years post operation, the Kaplan-Meier half 95% confidence width for the survival rate is given by:

$$\text{margin} = 1.96 \sqrt{[S(t)]^2[1 - S(t)]/N(t)}.$$

Based on published data, the annual infection rate of a normal shunt system is assumed to be 7.2%, then the 1-year infection free rate is 92.8%. With an enrollment of 130 patients and a dropout rate of 10%, by using the aforementioned formula, the sample size for infection free survival at one year post operation is given by:

$$N(1) = N_0 e^{-(r_1+r_2)} = 130 * e^{-(0.072+0.1)} = 109.$$

The half 95% confidence width of the survival given by:

$$\text{margin} = 1.96 \sqrt{[92.8\%]^2[1 - 92.8\%]/109} = 4.7\%.$$

The precision of 4.7% is less than 5% and is considered acceptable.

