#### **10.4 Criteria of qualification/disqualification of the trial results**

This study is to collect post-marketing safety data on the Chinese population implanted Hakim programmable shunt system, according to product registration requirements. The occurrence, type, severity, frequency, of all AEs occurring during the study period, as well as the correlation between AEs and the product will be collected and presented. Hence, criteria of qualification/disqualification were not applicable.

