#### **10.7 Report**

After the data of all subjects were completely collected (within one year after the operation), a clinical study report would be compiled and submitted to NMPA for review as material supporting the extension of product registration.

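### The symmetric Peto interval for one-year infection-free survival under-covers at some low infection rates (88–90% at 3% and 4%) and errs towards safety; a half-width below 5% is expected in one scenario, not ensured

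*Combined protocol and SAP*

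**What the plan says.** Section 10.6 (Endpoint analysis) estimates the one-year infection-free rate by Kaplan-Meier, and "the 95% confidence width for the survival rate will be estimated by the Peto method". It gives no formula. Section 10.3 does: "the Kaplan-Meier half 95% confidence width for the survival rate is given by" 1.96 × √(S(t)² × [1 − S(t)] / N(t)), where N(t) is the number still infection-free and under observation at t years.

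On precision, 10.3 says the study will "ensure 95% confidence bounds acceptable (half width < 5" per cent). It assumes 130 patients, 7.2% infection and 10% dropout, obtains 109 at risk and a margin of 4.7%, and concludes: "The precision of 4.7% is less than 5% and is considered acceptable". No other scenario is shown.

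Three other places set the context. Section 1.1 says of shunt infection in general that "Its incidence rate is 3-29" per cent. Section 10.2 says "The primary analysis will be descriptive in nature", and 10.4 that "criteria of qualification/disqualification were not applicable". Section 10.7 sends the report to the regulator as "material supporting the extension of product registration".

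**The concern.** There are two separate points.

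**Form of the interval.** The infection-free rate is expected to lie close to 100%. A symmetric interval on the raw scale behaves poorly there: the upper limit can pass 100%, the width is zero if no infection is seen, and the lower limit tends to sit too high. In a safety study the lower limit is the informative one, because it says how much infection the data still allow. If it is too high too often, the report overstates safety.

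**The word ensure.** A half-width that depends on the infection rate and on dropout cannot be ensured by a calculation at one value of each.

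There is no pass/fail criterion, so no decision rule is affected. What is at stake is whether the interval reported for the primary endpoint has the confidence level it claims.

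**Working it through.** **Inputs.** From 10.3: N₀ = 130, infection rate r₁ = 0.072, dropout rate r₂ = 0.10, multiplier 1.96. From 1.1: background infection range 3–29%. From 4.1: follow-up to 365 days. The timing of infections is not given, so two patterns were assumed: constant hazard and early onset.

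**The plan's figures reproduce.**
- N(1) = 130 × e^−(0.072 + 0.10) = 109.5 (the plan uses 109).
- Half-width = 1.96 × 0.928 × √(0.072/109) = 4.67%.

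**Direct behaviour of the formula.** Take N(1) = 109 and d infections, with S = 1 − d/130:

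| d | S | Half-width | Upper limit |
|---|---|---|---|
| 0 | 100% | 0 | 100% |
| 1 | 99.2% | 1.6% | 100.9% |
| 2 | 98.5% | 2.3% | 100.8% |
| 3 | 97.7% | 2.8% | 100.5% |

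Four infections are borderline: 96.92% + 3.19% = 100.1%.

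**Coverage by simulation.** n = 130, dropout rate 0.10, 100,000 studies per setting (simulation error about 0.1 point). Ranges span the two timing patterns.

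| True infection | Peto coverage | Peto lower limit above truth (nominal 2.5%) | Peto upper limit above 100% |
|---|---|---|---|
| 3% | 88–90% | 10–11% | 50–57% |
| 3.5% | 93–94% | | |
| 4% | 88–89% | 11% | 29–35% |
| 4.5% | 92–93% | | |
| 5% | 94–95% | | |
| 7.2% | 94–95% | 4–5% | 2–3% |

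Coverage rises and falls because the infection count is a small whole number. At 7.2% the misses are lopsided: 4–5% on the lower side against 0.7–0.8% on the upper.

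On the same simulated data, log-log limits with Greenwood variance (exact interval when there are no infections) cover 95–97% at all these rates. Their lower limit is above the truth in 0.2–1.4% of studies and their upper limit below it in 3–4%.

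**Dependence on dropout.** With complete follow-up, N(1) = 130 × S, and the half-width reduces to 1.96 × √(S(1 − S)/130), the ordinary Wald interval. Its exact binomial coverage is 89.8% at 3%, 89.0% at 4% and 90.0% at 7.2%. The near-nominal coverage at 7.2% therefore relies on dropout widening the interval.

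**Worked case (assumption: 3 infections and 18 dropouts spread evenly, leaving 130 − 3 − 18 = 109 at day 365).** Kaplan-Meier 97.5%; Peto 94.6% to 100.4%; log-log 92.5% to 99.2%.

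**Precision by the plan's formula, dropout rate 0.10.**

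| Infection | N(1) | Half-width |
|---|---|---|
| 3% | 114.2 | 3.1% |
| 4% | 113.0 | 3.5% |
| 7.2% | 109.5 | 4.7% |
| 8.4% | 108.2 | 5.0% |
| 10% | 106.4 | 5.4% |
| 29% | 88.0 | 8.0% |

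With infection held at 7.2%, the half-width reaches 5% at a dropout rate of 0.239: N(1) = 130 × e^−0.311 = 95.3, and 1.96 × 0.928 × √(0.072/95.3) = 5.0%. These are one-way limits, not a joint condition: 8.4% infection with a dropout rate of 0.24 gives 5.4%.

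Even when 7.2% and 10% are both exactly true, the realised half-width is below 5% in only about 70% of simulated studies.

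**The case against.** The strongest reply is that coverage is close to nominal at 7.2%, the only rate the plan assumes, and that 3% and 4% are troughs of an oscillating curve. The 3–29% range in 1.1 describes shunt infection in general and is not an assumption about this device. That is fair, and the result should not be read as 88–90% at every low rate. But the lopsidedness does not come and go in the same way: the lower limit is too high more often than 2.5% even at 7.2%, where total coverage looks acceptable.

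Second, the direction depends on censoring. If many charts end in the second half-year (assumption: 40% or 60% do, leaving about 75 or 50 at risk at day 365), Peto coverage becomes 90% or 97% at 3%, 97% at 4%, and 96% or 99% at 7.2%. This stands. The interval is then wider than needed: at 7.2% its half-width is about 6% or 7%. Log-log gives about 4.65% with early-onset infections and 5.1–5.4% with constant hazard.

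Third, an upper limit above 100% can be truncated, and zero infections in the whole cohort is rare: 0.97^130 is about 2% at 3% infection. Both are true. Truncation does not repair the lower limit, however. Zero events are also far more likely in the planned adult and child subgroups: with 30 children (an assumed number) and 3% infection the chance is 0.97^30 = 40%.

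Fourth, 10.3 states its inputs openly, and sizing on expected half-width is common practice. That is right, and it makes the second point one of wording: the plan should call the figure expected.

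Finally, log-log is not the only sound choice and is mildly lopsided the other way. It is nevertheless clearly closer to nominal than the planned interval.

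**Conclusion.** The concern holds. With 130 patients and 10% dropout, the planned interval covers 88–90% at a true infection rate of 3% and 88–89% at 4%, and nearly all misses there put the lower limit too high. At 7.2% total coverage is 94–95% with lopsided misses. The half-width below 5% is an expected value at one pair of assumptions.

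This rests on reading the Peto method in 10.6 as the symmetric formula in 10.3, the only one the documents give, and on the two assumed infection-time patterns, which agree closely. Heavy late censoring would turn under-coverage into excess width at most rates. Because the analysis is descriptive and has no success criterion, this is a change that should be made, not one on which the study stands or falls.

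**What to change.** **Section 10.6.** Replace the Peto sentence with: the Kaplan-Meier estimate at day 365 will be reported with Greenwood variance and a complementary log-log 95% confidence interval. This is an option in SAS PROC LIFETEST. Add: if no infection is observed, a two-sided 95% exact binomial interval will be given, with the number still at risk at day 365 as denominator. That denominator is conservative: the lower limit is 0.025^(1/109) = 96.7%, against 0.025^(1/130) = 97.2% if all 130 were used.

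**Section 10.3.** Replace the claim to ensure precision with: expected half-width 4.7% if one-year infection is 7.2% and dropout 10%; about 3.1% to 8.0% over the 3–29% background range at 10% dropout. Present that range as background for shunts in general. Label any smaller number at risk or subgroup size in a sensitivity table as an assumption.

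**Cost.** Two sentences and one software option, with no new data. Half the average interval width rises from 4.6% to about 4.7–4.8% at 7.2% infection, and from about 3.0% to 3.4–3.5% at 3%. Both limits must be reported, because a single margin no longer describes the interval.

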## **4. Research Design**

### **4.1 Basic design**

This study was designed to be single arm, multi-center, observational and retrospective. It is designed to gather information from actual clinical practice from the clinical records of patients in relation to the one-year clinical safety to the use of operation of Hakim programmable shunt system. The treatment date would be defined as the implant date of the Hakim programmable shunt system. The study period includes a general history period that includes up to 30 days prior to the treatment date and a follow-up period of up to 365 days post implant operation. A total of 130 patients would be enrolled and adverse events would be collected for subjects enrolled within one year after the implantation of Hakim programmable shunt system from April 01, 2017 to August 31, 2019, through case review or hospital database (if any).

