### 6.2 Inclusion criteria

Subjects who met all of the following inclusion criteria would be enrolled:

1. The informed consent was exempted by the Ethics Committee of a research center. Or a subject or his/her legal representative signed the informed consent form (ICF) prior to the enrollment;
2. A subject had an indication suitable to use Hakim programmable shunt system;
3. A subject received a Hakim Shunt Programmable System at least one year ago.

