## 7 Research Process

The research process included: Screening and enrollment of subjects, Days -30 to -1 before the operation, Day 0, the day of operation, and one-year follow-up (Days 1-365) after the operation.

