## **8.4 Duration of follow-up after an adverse event**

As this is a retrospective study, it did not intervene in subjects' normal treatment. Therefore, all adverse events were properly evaluated by an investigator based on medical requirements. And no additional follow-up would be performed.

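### Does the Peto interval at one year need a written rule for who counts as at risk on Day 365?

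*Combined protocol and SAP*

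**What the plan says.** Section 10.3 (Sample size) defines N(t) as roughly the number of subjects left infection-free at t years once infection and dropout have both been removed. It sets the Peto half-width as 1.96 × √(S²(1 − S)/N(t)). With 130 enrolled, a 7.2% annual infection rate and 10% dropout, it obtains N(1) = 109 and a half-width of 4.7%, and concludes: "The precision of 4.7% is less than 5% and is considered acceptable".

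The Endpoint analysis part of section 10.6 carries the method into the analysis: "the 95% confidence width for the survival rate will be estimated by the Peto method". It does not restate N(t), and it gives no censoring date and no rule for death without infection.

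On the window, section 4.1 has "a follow-up period of up to 365 days post implant operation" and section 7 has "one-year follow-up (Days 1-365) after the operation". Section 8.4 adds that "no additional follow-up would be performed". Section 6.2 requires that "A subject received a Hakim Shunt Programmable System at least one year ago". Section 10.7 times the report as follows: "After the data of all subjects were completely collected (within one year after the operation").

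Three other places bear on the point. The Schedule of Data Collection Form includes an end-of-study or exit record. Section 11.3.1 requires source documents to show all follow-up information and the subject's condition at completion or withdrawal. Sections 10.2 and 10.4 make the primary analysis descriptive and say that criteria for a qualified or disqualified result do not apply.

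**The concern.** The Peto variance uses only the number at risk at the evaluation time, and here that time is the last day of the window. Follow-up comes from existing records, and few patients happen to attend on Day 365 itself. Suppose one analyst censors each uninfected patient at the last contact inside the window. A patient last seen on Day 350 then drops out of N(1), even if a visit on Day 380 was clean. Suppose another analyst treats a completed end-of-study record as observation to Day 365. Nearly every uninfected patient then counts. The estimated rate would be almost the same, but the two intervals could fall on opposite sides of 5%, the only numerical target in the design.

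Two passages seem to sharpen the problem. Section 10.7 can be read as saying that data collection itself finishes within a year of surgery, which would rule out any later contact. Section 7.4 calls a patient who died within the year a complete case, without saying how that patient enters the risk set. At stake would be the width of the interval reported to the regulator, and possibly a return to the charts to find missing last-contact dates.

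**Working it through.** **Inputs.** From section 10.3: N₀ = 130, r₁ = 0.072, r₂ = 0.10, S(1) = 0.928, multiplier 1.96, target half-width below 5%. The share of patients with a record reaching Day 365 is not in the documents and is varied below as an assumption.

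**1. The plan's own figures.**
- N(1) = 130 × e^−(0.072 + 0.10) = 109.46, stated as 109.
- Half-width = 1.96 × 0.928 × √(0.072/109) = 4.67%, stated as 4.7%.

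Both reproduce.

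**2. Smallest count that meets the target.** N = 0.072 × (1.96 × 0.928/0.05)² = 95.28, so 96. The half-width is 4.98% at 96 and 5.01% at 95. Expected uninfected patients are 130 × 0.928 = 120.6, and 120.6 − 96 = 24.6. So up to 24 of them (about 20%) may go uncounted. The planned 109 leaves a margin of 13.

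**3. Half-width by the share of uninfected patients not counted at Day 365** (S held at 92.8%):

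| Share not counted | N(1) | Peto half-width |
|---|---|---|
| 0% | 120.6 | 4.44% |
| 10% | 108.6 | 4.68% |
| 20% | 96.5 | 4.97% |
| 30% | 84.4 | 5.31% |
| 50% | 60.3 | 6.28% |

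**4. Effect on the estimate.** I simulated 3,000 studies of 130 patients at 7.2% risk with exponential infection times. Half of the patients were censored in Days 335–364 and the rest on Day 365. The mean Kaplan-Meier rate was 92.8%, the mean N(1) about 60 and the mean Peto half-width 6.2%. The mean Greenwood half-width on the same data was 4.4%. The sensitivity therefore lies in the Peto denominator; the rate is hardly affected.

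**5. Chance alone.** With complete follow-up, N(1) = 130 × S, and the Peto formula reduces to 1.96 × √(S(1 − S)/130). With 12 infections S = 118/130 and the half-width is 4.98%. With 13 infections S = 117/130 = 0.90 and it is 1.96 × 0.90 × √(0.10/117) = 5.16%. The binomial probability of 13 or more infections among 130 at 7.2% is 14%. In the simulation, 14% of studies with no early censoring reached 5% or more.

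**6. Neither censoring rule is free of bias.** True risk is 7.2%; λ = −ln 0.928 = 0.0747 and, at 10% loss, θ = −ln 0.90 = 0.1054.
- Charts that stop early are carried to Day 365 as uninfected: apparent risk = λ/(λ + θ) × (1 − e^−(λ+θ)) = 0.415 × 0.165 = 6.8%.
- Patients are censored at last contact, but only well patients' charts stop early. The hazard at time t is then λe^(−λt) divided by (e^(−λt) − 0.928 + 0.928e^(−θt)), which integrates over the year to an apparent risk of 7.6%.

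The errors run in opposite directions and are about the same size.

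**7. The passages side by side.** Section 6.2 requires implantation at least a year before enrolment, so collection cannot close within a year of surgery. The parenthesis in section 10.7 must describe the period that the data cover. Day 365 is the end of the observation window, and charts are read after it.

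**The case for a change.** The strongest case for a change is that a planning assumption of 10% dropout does not tell an analyst which charts are dropouts, and that section 10.6 fixes a method whose width rests wholly on that count. A few sentences would settle it, and doing so before charts are closed is easier than after. The interval also goes to the regulator, and the plan itself justifies its sample size by the 5% limit.

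The first part stands: the rule is unwritten, and the Peto interval is more exposed to it than a Greenwood interval would be. The rest carries less weight. Under the usual Kaplan-Meier convention a patient censored on Day 365 is at risk on that day, and a patient whose record shows no infection through the window is censored there. Nothing in sections 10.3 or 10.6 directs an analyst to exclude a patient because no visit fell exactly on Day 365. The exit record and the required note of condition at completion or withdrawal point to the information needed. The case report form is not shown, so its fields cannot be assumed absent. Records are kept for at least ten years under section 11.3.4, so a missing date could still be recovered.

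The wording on death in section 7.4 is a fair query, but it concerns completeness of the record. Whether death without infection should be a competing event is a separate question, and the documents give no death rate from which to size it.

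**Conclusion.** No change is needed. The plan leaves out a definition that a competent analyst would fill in the ordinary way: observation to Day 365 for patients known to be infection-free through the window, and censoring at last contact for those lost earlier. That agrees with section 10.3, which already takes dropouts out of N(t). The planned 109 and 4.7% are correct.

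The half-width passes 5% at S = 92.8% only if more than about 20% of uninfected patients go uncounted at Day 365, twice the planned dropout. The larger figures, such as 6.3%, rest on an assumed pattern of contacts that no passage supports. The 5% served to choose the sample size. It decides nothing at the analysis, and chance alone would exceed it about one time in seven. Writing down one censoring rule in place of another would exchange one small bias for its opposite.

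This conclusion assumes that exit records separate patients followed through the window from those lost before it, and that infection risk is near the planned 7.2%. Showing the number at risk under the Kaplan-Meier curve, with a Greenwood interval alongside, would be good reporting practice; it does not require a change to the plan.
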